a 3-5 point change out of 100) on the PROMIS physical functioning measure can be detected with 50-65 patients per practice. Based on prior experience, we expect a minimum 50% response rate for completing the first patient survey and a 65% response rate for the second survey. We expect a 3% rate for undeliverable addresses and a 20% drop-out rate between the two survey periods based on our previous research. Patient-level blood pressure data from adult diabetic patients at HCP ACO practices were used to calculate the design effect (ICC=0.01-0.02). Previous research suggests that population-level improvements in blood pressure on the order of 3-5 mm Hg are clinically meaningful⁴⁸⁻⁵⁰. Based on a two-sided difference of means with a power of 0.90, we estimate that an average of 140 patients per practice are needed to detect a 3 mm Hg difference in change in systolic blood pressure over time between the high (n=8) vs. low (n=8) PA&E practices. Based on these calculations, we will randomly select 273 patients per practice (n=4,368) with diabetes or CVD diagnoses from each of the practice sites and teams in the two ACOs for inclusion in the study. Given the assumptions of response rates and attrition noted above, this will yield a final total of 1102 patients with two time points for analysis of the PROMIS (69 patients per site). In addition we expect to receive retrospective clinical outcomes data from the EHR for most of the sampled patients (n=4,368). Thus, even with slightly lower than expected survey response rates, our study will be sufficiently powered to detect clinically meaningful differences between high and low PA&E practices on both patient-reported (PROMIS) and clinical, e.g., blood pressure, outcome measures.

MEASURES

Measurement of Site PA&E Activities

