Patient Reported Outcome Measure – PACIC-11

The Patient Assessment of Chronic Illness Care scale (PACIC-11) developed and validated by Glasgow et al⁵⁸ (Medical Care, 2005; see Appendix II) will be used to assess the extent to which practices engaging in more PA&E activities and with higher team functioning will be able to effectively improve patients' experiences of chronic illness care over time. The PACIC-11 has high Cronbach's alpha internal consistency, reliability of 0.93, and reasonable test-retest reliability of 0.58. It also demonstrates convergent validity with the Hibbard PAM measure and several dimensions of the Ambulatory Care Experiences Survey (ACES), the precursor to the Clinician Group Consumer Assessment of Healthcare Providers and Systems (CG-CAHPS) survey ([name] and Crane 2011)⁵⁹. We will supplement the PACIC-11 with selected items from the Ambulatory Care Experiences Survey (ACES) focused on patients' experiences of primary care teams ([name], Rogers et al., 2007)⁶⁰. (See Appendix II)

Clinical Measures

Based on each site's EHR, we will have de-identified data for blood pressure, lipids, and HbA1c to measure percentage of hypertensive patients with blood pressure controlled (<140/90 mm Hg), percentage of patients with diabetes with blood sugar controlled (HbA1c <8.0%), and percentage of patients with cardiovascular conditions or diabetes whose lipids are controlled (LDL-C <100 mg/dL). The patient survey sampling frame includes "established" patients of each primary care physician and team. The adult diabetic and CVD patients will need to have at least two primary care visits in the baseline year (2013) to improve the reliability of reports of patients' experiences of care and to focus on an established patient population that has a high propensity to maintain clinical relationships and receive routine primary care over time. Since attribution of patients to practices and PCPs is a contentious issue in performance measurement in improvement^{61, 62}, restricting the sample to patients with diabetes and/or CVD who have ongoing relationships will also aid in team acceptance of the feedback data.

Patient Demographics

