The two ACOs will also securely transmit a de-identified patient-level data to the UC Berkeley research team in Months 7 and 19 covering 2014 and 2015 period, respectively. The dataset will include adult patients with diabetes, cardiovascular disease, and/or asthma with at least 2 visits in the baseline year (2014) and the data elements include select sociodemographic information and clinical care process and outcome data using Healthcare Effectiveness Data Information Set (HEDIS) definitions for measures of chronic illness care.

PRINCIPAL INVESTIGATOR (LAST, FIRST, MIDDLE): [name]

For analysis of all patient-level data at UC Berkeley, we will create unique subject identifiers that do not include date of birth, social security number, or medical record number. The ACOs will be responsible for linking each patient's EHR data to their study ID, and thus the data transmitted will not be identifiable to any researchers or staff at UC Berkeley. All such de-identified data will be housed at Berkeley on password-protected, secure servers accessible only by Principal Investigator [name] and the Co-Investigators and staff under his direction.

Advocate Health Care and HealthCare Partners will also provide the UC Berkeley research team with the names, emails, and mail contact information for all primary care clinicians and staff of the eight practices so that a survey of team culture, leadership, relational coordination, and perceived team effectiveness can be conducted at two points in time (between months 0-6 and between months 13-18).

These two ACOs will also work with the UC Berkeley team to coordinate two site visits lasting two to three days for the research team to interview key people, some patients, and to observe meetings. Finally, the ACOs will assist with recruiting five patient representatives from the target population to serve on an advisory board that will provide recommendations and feedback for the ACO practices to consider as they refine and improve their PA&E efforts.

Sources of Materials

Advocate Health and HealthCare Partners will be responsible for linking patients' EHR data to their study ID, and thus the data transmitted will not be identifiable to any researchers or staff at UC Berkeley.

As described above, Quantum Market Research (QMR) will receive identifiable patient information such as name, address, and phone number directly from Advocate and HealthCare Partners only for the purposes of administering the survey.

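### The clinical outcomes are defined as percent controlled, but the only clinical power figure is for mean change in systolic pressure, so the stated 0.90 does not apply to them

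*Combined protocol and SAP*

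**What the plan says.** Clinical Measures (under Measures) is the only place where the clinical outcomes are given an operational definition: "we will have de-identified data for blood pressure, lipids, and HbA1c to measure percentage of hypertensive patients with blood pressure controlled (<140/90 mm Hg". The same sentence defines HbA1c as the percentage of patients with diabetes below 8.0%, and LDL-C as the percentage of patients with cardiovascular conditions or diabetes below 100 mg/dL.

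Patient Selection gives the only clinical power statement. "Based on a two-sided difference of means with a power of 0.90", the plan puts the requirement as follows: "an average of 140 patients per practice are needed to detect a 3 mm Hg difference in change in systolic blood pressure over time". The comparison is of 8 high-PA&E with 8 low-PA&E practices. The clustering input comes from one of the two ACOs: "Patient-level blood pressure data from adult diabetic patients at HCP ACO practices were used to calculate the design effect", with an ICC of 0.01-0.02. The Berkeley human-subjects section repeats the calculation. Both places then conclude that power is adequate for clinical outcomes, with blood pressure as the example.

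The Analysis Section enters ClinMeasures in the Aim 1, 2 and 4 equations without stating a scale or link function. The human-subjects section for the two ACOs describes the transferred data as "clinical care process and outcome data using Healthcare Effectiveness Data Information Set (HEDIS) definitions for measures of chronic illness care", and Consortium Contractual Arrangements uses the same description. Neither says whether the numeric results are included.

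**The concern.** A proportion below a cut-off and a mean in mm Hg are different endpoints. A calculation for one says nothing about the other unless a control rate and a percentage-point effect are supplied, and the plan supplies neither. A systolic pressure that falls from 165 to 145, or an HbA1c that falls from 10.5% to 8.2%, changes the numeric outcome but not the defined one.

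Clinical outcomes are part of the central question and of Aims 1, 2 and 4. If the percent-controlled measures are analysed as defined, a 3 mm Hg difference, the lower end of what the plan calls clinically meaningful, might be missed. It could then be reported as no effect of PA&E on the strength of a 0.90 that was never calculated for that outcome. If the numeric values are what is meant, the definition and the data specification need to say so before data are transferred.

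**Working it through.** **Inputs from the plan.** Two-sided difference of means, power 0.90, 3 mm Hg, 8 v 8 practices, 140 per practice, ICC 0.01-0.02. EHR data are expected for most (Patient Selection) or all (Berkeley human-subjects section) of 4,368 patients, so up to 4,368/16 = 273 per practice.

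**Inputs assumed, because the plan does not give them.** Alpha 0.05; SD of systolic level 16 mm Hg; mean 130, 135 or 140 mm Hg; systolic cut-off only.

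**1. The plan's own figure.** Design effect = 1 + (m − 1) × ICC. Effective n per group = 8m / design effect. SD of change = 3 × √(effective n / 2) / (1.960 + 1.282).

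- ICC 0.01: design effect 1 + 139 × 0.01 = 2.39; effective n 1120/2.39 = 468.6; SD 14.2 mm Hg.
- ICC 0.02: design effect 1 + 139 × 0.02 = 3.78; effective n 1120/3.78 = 296.3; SD 11.3 mm Hg.

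With a t reference on 14 df the SDs are 13.2 and 10.5. So 140 is consistent with an SD of change of about 10.5-14.2 mm Hg. With no SD or alpha stated, it can be neither confirmed nor contradicted.

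**2. The same shift on both scales, by simulation.** Systolic pressure at two waves; a practice effect on change with ICC 0.01 or 0.02; SD of change set at 13.1 or 10.4, so that the numeric analysis has 0.90 power at 140 per practice; every patient in the high group shifted by 3 mm Hg. The test is a two-sided t-test on 16 practice means (14 df), with 3,000 trials per setting. On the cut-off scale, 3 mm Hg appears as about 6-8 percentage points.

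| Patients per practice | Mean change in systolic BP | Change in percent <140 |
|---|---|---|
| 140 | about 0.90 | 0.63-0.75 |
| 273 | 0.93-0.96 | 0.81-0.87 |

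**3. Sensitivity of step 2.**

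- Level SD 14-20 at mean 135: 0.63-0.74 at 140 and 0.81-0.87 at 273 on the cut-off scale.
- Second-wave status adjusted for first-wave status: about 0.73-0.80 at 140 and 0.87-0.92 at 273.
- Same 3 mm Hg average, but confined to patients at or above 140 at baseline (6-11 mm Hg in them, an extreme case): cut-off 0.75-0.97 at 140 and 0.89-0.995 at 273; numeric value 0.89-0.92 and 0.92-0.95.
- If 50-70% of the 273 were hypertensive (assumed, mean 135): cut-off 0.68-0.78.

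**4. Closed-form cross-check at one time point.** p2 = Φ(Φ⁻¹(p1) + 3/SD). Power = Φ{[(p2 − p1)√n − 1.96√(2p̄q̄)] / √(p1q1 + p2q2)}, where n is the effective n per group. This treats the back-solved SD of change as the SD of level, which favours the cut-off measure.

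Take p1 = 0.60 and ICC 0.01. Then p2 = Φ(0.253 + 3/14.17) = 0.679, and at 140 per practice power = Φ{(0.0791 × 21.65 − 1.96 × 0.679)/0.677} = Φ(0.56) = 0.71. At 273 the effective n is 2184/3.72 = 587.1 and power is 0.81. With ICC 0.02, p2 = 0.698 and power is 0.71 and 0.77. If the ICC is itself attenuated by the cut-off (0.006 or 0.012), power is 0.82 or 0.85 at 140 and 0.92 or 0.91 at 273. With the unattenuated ICC, the difference detectable from 60% at 0.90 power is 10.1-12.5 points at 140 and 9.0-11.8 points at 273.

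**The case against.** The strongest reply is that the mismatch need not cost much. The 140 is a calculated requirement. The planned EHR sample is up to 273 per practice, where the illustrative power on the cut-off scale is 0.81-0.87, and higher with adjustment for baseline status. A uniform shift favours the numeric scale; if practices act mainly on uncontrolled patients, percent controlled can do as well or better. Control rates also look deliberate, since the Significance section motivates the study with them. All of this stands, and it limits what can be said about size. It does not supply a power figure for any percent-controlled measure.

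Three stronger readings are tempting but not supported.

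- A reader might infer that power for percent controlled is well below 0.90. That rests on an SD, a control rate and an effect pattern that the documents do not give.
- A reader might infer from the HEDIS wording that only met/not-met flags will be sent. The plan does not say so, and the study design text and Sources of Materials speak of obtaining measures of blood pressure, HbA1c and LDL-C. The gap is that numeric transfer is not specified.
- A reader might infer that every Aim 4 analysis reduces to a change of −1, 0 or +1. Aim 4 also lists lagged regression, and the Aim 1 comparison is cross-sectional.

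Nor is it established that restriction to hypertensive patients must lower power further: fewer patients lower it, but a mean nearer 140 raises it.

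**Conclusion.** The concern holds as a mismatch between the defined outcomes and the powered quantity. The 0.90 belongs to mean change in systolic pressure alone. Percent controlled has no power figure, HbA1c and LDL-C have none on any scale, and the general statement that clinical outcomes are adequately powered goes beyond the calculation. This follows from the text and needs no assumption.

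The size of the loss is illustrative: under a uniform shift and the assumptions listed above, from about 0.90 to 0.63-0.75 at 140 per practice, and from 0.93-0.96 to 0.81-0.87 at 273. It is smaller with baseline adjustment and may be nil if the effect is concentrated in uncontrolled patients. The figure of 273 is a ceiling for blood pressure and HbA1c, whose eligible numbers are not stated. The simulations ignore diastolic pressure and use practice means, not the planned multilevel models with casemix. Confidence in the overall point, including its size, is moderate.

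**What to change.** - **Clinical Measures:** define the main analysed clinical outcomes (ClinMeasures, Aims 1-4) as patient-level numeric values: systolic pressure, with diastolic also reported; HbA1c in patients with diabetes; and LDL-C. Keep the percent-controlled measures as secondary outcomes and for practice feedback.
- **Data transfer (human-subjects section for the two ACOs, and Consortium Contractual Arrangements):** specify that numeric results and their dates are sent.
- **Patient Selection and its repeat in the Berkeley human-subjects section:** state that the 0.90 refers to mean change in systolic pressure only, and give the SD, alpha and eligible number per practice. Do not extend the claim of adequate power to percent controlled, HbA1c or LDL-C without a calculation for each.

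If percent controlled is to remain the main outcome, the minimum is to say so and give power on that scale, with the control rate, ICC, alpha and eligible number.

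The cost is one paragraph in Measures, one line in each data specification and an edit to the power text, with no added patients or tests. The downside is that the familiar quality metric becomes secondary.

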We posit that practices that have more highly developed PA&E and better teamwork will more effectively activate patients with diabetes and/or CVD. In turn, we posit that more highly activated patients will be more likely to achieve improvements on patient-reported outcomes, patient care experiences, and clinical measures over time compared to less activated patients. We also will also examine the roles that patient advisory groups and primary care team use of performance feedback data play in influencing improvements in patient activation and outcomes of care over time.

Figure 1. Logic Model

We will engage patients and primary care practice teams within two accountable care organizations (ACOs). In each ACO, we will randomly select eight practices: four who score high on PA&E activities and four who score low. We will survey practice team members twice: once at baseline and one a year later. We will also conduct two site visits: one near the beginning of the study and one during the 13-18 month period of the study.

[figure not shown]
We will randomly select four high and four low PA&E sites within each ACO using a broad definition of PA&E activities including: (1) patient care outreach in regard to disease prevention and health promotion; (2) changes in the clinician-patient relationship, particularly in the areas of communication, motivational interviewing, and patient involvement in treatment care plans; (3) shared decision-making; (4) patient self-management of their condition(s); (5) end of life/advanced serious illness care patient engagement and family involvement; and (6) patient involvement in the overall design of care and in organization-wide efforts to improve the quality of care. See methods section for a description and Appendix I for an example of the instrument to be used for determining the “more highly involved” and “less highly involved” practices.

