ACO Established	MSSP: July, 2012 AdvocateCare (Commercial): 2011	MSSP: January, 2014 Cigna (Commercial): April, 2013 Anthem (Commercial): July 2013
Location	Illinois	Senior ACO (MSSP): CA, FL, NV Commercial ACO: Greater Los Angeles, CA, NV (Cigna)
Patient population	MSSP: 106,000 Commercial: 370,000	Senior (MSSP): 56,689 Commercial: 65,739
ACO Contract Lives	MSSP: 106,000 Commercial: 370,000	Senior (MSSP): 56,689 Commercial: 65,739

PRINCIPAL INVESTIGATOR (LAST, FIRST, MIDDLE): [name]

Patient Race/Ethnicity	57% Non-Latino White 22% African American 8% Latino 5% Other/multi-racial 3% Asian/Filipino 1% American Indian/Alaska Native 1% Middle East 1% Eastern Indian 2% Unknown/Declined	
 55% Latino 25% Non-Latino White 15% Asian/Pacific Islander 10% African-American 	CLINIC/PRACTICE SELECTION Advocate ACO and HealthCare Partners ACO have 150 and 69 primary care practice sites, respectively. Using the list of PA&E activity domains previously described (see Appendix I for a draft of the checklist instrument), we will randomly select four practices from each ACO that score in the top quartile of the PA&E activities and four practices from each ACO that score in the bottom quartile. This will maximize the difference between those practices with high involvement and those with little or no involvement.
Payer Mix	
 Commercial: 70% Medicare Advantage: 5% Advocate Employee: 5% Medicare ACO: 20% 	
 HCP commercial: 68% HCP Medicaid: 13% HCP Senior: 19% 	
ACO Risk Arrangement	
 Shared savings (no risk) 	
 Shared savings (no risk) 	

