To project the sample size requirements given 16 practices (8 high PA&E and 8 low PA&E), we estimated the design effect (DE) to account for the clustering of patients within practice sites. While PROMIS data from participating ACO patients are presently unavailable, recent studies of change over time on the PROMIS physical functioning measure informed our sample size estimates for the PROMIS measure⁴⁷. Having been selected using item-response theory (IRT) methods and extensive testing, the PROMIS physical functioning measure is a precise measure that is sensitive to small changes in physical functioning over time. Given the published estimates and a range of design effect estimates (intraclass correlation (ICC)=0.01-0.04) to account for the clustering of patients within practices, a clinically meaningful change (e.g.,

PRINCIPAL INVESTIGATOR (LAST, FIRST, MIDDLE): [name]

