We will categorize the more than 150 Advocate ACO primary care practice sites and the 69 HCP ACO practice sites as high vs. low PA&E involvement based on a brief 40-item practice assessment of the six domains of PA&E activities (see Appendix I). This list was developed in consultation with a National Advisory Committee to our study of ACO involvement in PA&E and the preliminary results of the survey (see page 2) supported by the Gordon and Betty Moore Foundation. This checklist instrument, including measures of the degree of implementation, will be completed by the person most knowledgeable about each practice's PA&E activities. Based on past experience this will be the Chief Medical Officer or Quality Improvement leader. Each of the ACOs practices will be categorized into quartiles based on their overall PA&E score. We will then sample practices for involvement from the top and bottom quartiles to finalize four highly involved PA&E practices and four low involved PA&E practices within each of the two ACOs for engagement in the research study.

Patient Activation (PAM)

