Analyses Addressing Aim 1. At each of the two cross-sections for the patient and teamwork assessment surveys, we will clean the data, examine their distributions, and conduct psychometric analysis to assess the reliability and validity of the measures. After composite variables have been constructed and properties assessed, we will examine the cross-sectional relation of PA&E activities, teamwork assessment results, and patient survey results. Using a dichotomized variable derived from baseline responses to the PA&E Practice Site Assessment Survey (see Appendix I), we will categorize sites as “high” or “low” PA&E based on the response distributions in our data. We will then assess association of key measures in two stages. In the first equation, using linear regression models, we will examine the PAM as a function of high vs. low PA&E (site level), controlling for practice size, and for patient casemix adjustment variables previously used in research that has compared organizations on patient experience and clinical quality measures^{79, 80}. Casemix factors to be considered include age, sex, educational attainment, and comorbid health conditions. We will then examine the patient reported outcome (PRO) measures, patient experience (PE) and the clinical measures as a function of the PAM, PA&E level (at site level), practice size, and casemix using multilevel regression models to account for the clustering of patients within practices. The simplified equations are:

$$PAM = Hi / lowPA \& E + PracticeSize + Casemix + \epsilon$$

$$PE = Hi / lowPA \& E + PAM + PracticeSize + Casemix + \epsilon$$

$$PRO = Hi / lowPA \& E + PAM + PracticeSize + Casemix + \epsilon$$

$$ClinMeasures = Hi / lowPA \& E + PAM + PracticeSize + Casemix + \epsilon$$

Aim 2. To assess whether the relation of PA&E activities and better PROs and clinical outcomes is stronger for more highly activated patients than less activated patients at baseline.

Analyses Addressing Aim 2. To address the extent to which PA&E activities conducted by the practice are more influential in improving PROs and patient experience among patients with high PAM levels at baseline, we will extend the Aim 1 analyses. Specifically, we will use multilevel regression with site random effects to model changes in PROs and the clinical measures over time as a function of baseline PAM scores, practice size, patient casemix, PA&E, and then by interacting PA&E and the PAM scores. The simplified equations are:

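### The high/low PA&E exposure in the models is defined by an unspecified cut in the data, not by the quartile groups from which practices were selected, so the ACO balance built into the design is not secured

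*Combined protocol and SAP*

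**What the plan says.** **Selection.** The Research Plan fixes the design within ACO: "In each ACO, we will randomly select eight practices: four who score high on PA&E activities and four who score low". The Clinic/Practice Selection text adds the quartiles. For the high group, the team will "randomly select four practices from each ACO that score in the top quartile of the PA&E activities". The low group is drawn in the same way, again four per ACO, from the lowest quartile. Under Measurement of Site PA&E Activities, the quartiles come from the Appendix I checklist: "Each of the ACOs practices will be categorized into quartiles based on their overall PA&E score". The natural reading is quartiles within each ACO, although no sentence says so outright. The Patient Selection section plans the sample as 8 high against 8 low practices.

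**Analysis.** The Aim 1 analysis builds the exposure anew: "Using a dichotomized variable derived from baseline responses to the PA&E Practice Site Assessment Survey", sites are to be called high or low "PA&E based on the response distributions in our data". It does not say where the cut lies, whether it is found among the 16 study practices or all 219 screened, or whether it is set separately in each ACO. The Aim 1 and Aim 2 equations contain the high/low term, PAM (as outcome or covariate), practice size and casemix. None contains a term for ACO.

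**The concern.** The study's main exposure has two descriptions, and nothing in the documents states that they give the same grouping. After sampling from opposite quartiles no new dichotomy is needed: each practice already has a label, and four plus four per ACO makes the groups equal in their mix of ACOs.

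That equality matters because the two ACOs differ greatly. Table 2 shows 8% Latino patients at one and 55% at the other, and lists Medicaid (13%) only at the second. The background section says that Latino patients are less likely to reach glycemic, cholesterol and blood pressure goals, which are the study's clinical outcomes. The casemix factors named for Aim 1 (age, sex, education, comorbidity) include neither ethnicity nor payer. With no ACO term, the 4+4 balance is the only explicit protection against confounding by ACO. A random effect for site does not replace it, since it does not adjust the group contrast for a mean difference between ACOs.

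A pooled cut can move practices in one direction only: high practices of the lower-scoring ACO become low, or low practices of the higher-scoring ACO become high. Either way, group becomes partly a marker of ACO.

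**Working it through.** **1. The plan's own figures.** 4 high × 2 ACOs = 8 and 4 low × 2 ACOs = 8. The planned yield reproduces: 273 × 16 = 4,368, and 4,368 × 0.97 × 0.50 × 0.65 × 0.80 = 1,101.6, the stated 1102 (69 per practice). The 140 patients per practice for blood pressure cannot be reproduced, because neither the SD of change nor alpha is given. Step 5 therefore uses relative power only.

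**2. How far apart must the ACOs be?** Assume normal scores with equal SD and quartiles within ACO. The quartile limits lie 0.674 SD either side of each ACO's mean.
- Cut at the median of the 16: a practice can move only when the upper limit in the lower ACO falls below the lower limit in the higher ACO, so at a difference of about 2 × 0.674 = 1.35 SD.
- Cut near the centre of all 219: with a difference of d, the centre lies about (150/219) × d = 0.685d from the mean of the smaller ACO. Its practices start to move at about 0.674/0.685 = 0.98 SD. Sampling variation brings occasional moves down to about 0.75 SD.

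**3. Simulation.** 150 and 69 practices, normal scores, four drawn from each ACO's own top and bottom quartile, then one pooled cut; 4,000 runs per setting. The ranges reflect whether the quartile size is rounded down or up (37 or 38 practices, and 17 or 18) and which ACO scores higher. Chance that at least one of the 16 changes group:

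| ACO difference (assumed) | Median of the 16 | Mean of the 16 | Median of all 219 |
|---|---|---|---|
| 0 to 0.5 SD | about 0 | under 1% | under 1% |
| 0.75 SD | about 0 | 1–2% | 3–7% |
| 1.0 SD | under 1% | 7–10% | 24–34% |
| 1.5 SD | 26–34% | 54–62% | 86–90% |
| 2.0 SD | 84–90% | 94–96% | 99% |

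At 1.5 SD with the median of all 219, on average 1.7 to 1.9 practices change group.

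**4. Confounding by ACO.** With no ACO term, the fraction of an ACO outcome difference that enters the high-low contrast is (share of one ACO in the high group) − (its share in the low group).
- Selection labels: 4/8 − 4/8 = 0.
- One practice switched: 5/9 − 3/7 = 0.13.
- Two switched, same ACO: 6/10 − 2/6 = 0.27.
- One switched in each ACO (8 vs 8 kept): 5/8 − 3/8 = 0.25.
- Two switched in each ACO (8 vs 8 kept): 6/8 − 2/8 = 0.50.

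For illustration, suppose the ACOs differed by 3 mm Hg in change in systolic pressure (an assumption). Two switches in one ACO would then add about 3 × 0.27 = 0.8 mm Hg to a contrast planned to detect 3 mm Hg. Adjustment for practice size and casemix could absorb some of this.

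**5. Power.** Calibrated to 0.90 at 8 vs 8 with two-sided alpha 0.05 (assumed), power at h vs l practices is Φ(3.242 × √[0.25/(1/h + 1/l)] − 1.960). This gives 0.895 at 7 vs 9, 0.881 at 6 vs 10, 0.852 at 5 vs 11 and 0.802 at 4 vs 12. A median split of the 16 keeps 8 vs 8 unless scores are tied. At 1.5 SD, the mean of the 16 departs from 8 vs 8 in about half of the runs (49–55%), and the median of all 219 in 86–90%.

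**The case against.** The strongest reply is that no regrouping is stated. Selection and analysis use the same baseline Appendix I checklist, Table 3 shows a single Wave 1 PA&E survey alongside the finalizing of practice enrolment, and quartiles are themselves a feature of a response distribution. The Aim 1 sentence may be no more than a loose restatement of the selection rule. The harm also needs three conditions together: quartiles formed within ACO, a pooled cut in the analysis, and a large ACO difference. Had the quartiles been formed over all practices, a pooled median could not move any selected practice. All of this stands, and it limits the point to an exposure definition that should be settled.

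Three stronger readings are tempting, and the documents do not support them.
- *The analysis will regroup practices.* The text permits this but does not say it; the pooled cut is one reading.
- *The 8 vs 8 comparison is broken.* A median split of the 16 keeps it and can lose only the balance within ACO. Where other cuts lose it, one or two switches cost at most about 0.02 of power.
- *The cut will be fitted to the outcomes.* Table 3 does place the Wave 1 analysis after the first patient survey. But the Aim 1 text bases the cut on baseline exposure responses and puts categorization before the association models.

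What the reply does not remove is that no sentence carries the selection labels into the models, and the words used describe a different rule.

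**Conclusion.** The point holds as an unspecified exposure definition with a conditional harm. The design-based grouping has zero imbalance by ACO whatever the scores turn out to be. The rule written for the analysis does not guarantee this. Under a pooled cut, switching is negligible up to an ACO difference of 0.5 SD. At 1.0 SD it affects from under 1% to 34% of studies, and at 1.5 SD 26% to 90%, depending on the cut. These figures rest on normal scores, equal SDs, within-ACO quartiles and an assumed ACO difference that the documents neither give nor exclude. If practices do switch, confounding by ACO is the main consequence and loss of power a minor one. This is a small, free improvement and does not call the design into question.

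**What to change.** In the Aim 1 analysis, replace the data-based categorization with a statement that high/low in all models is the quartile group from which the practice was selected, four high and four low in each ACO. In the same edit, state that the selection quartiles are formed within ACO, if that is the intention.

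Add an ACO fixed effect to the Aim 1 and Aim 2 equations. It uses one practice-level degree of freedom and protects the contrast if a practice drops out and upsets the balance. On its own it would not settle which practices count as high.

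Use the continuous 0 to 40 PA&E score, already planned for Aim 5, as a sensitivity analysis for the outcome models, with no second cut-point.

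The cost is a few sentences: no new data, no change to practice selection and no change to sample size. The change is best made before any Wave 1 outcome is analysed.
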